8.12.1.2 List of adverse drug reactions

As reported in the summary of product characteristics for 25mg temsirolimus i.v. (mostly from clinical information on renal cell carcinoma patients):

System organ category	Preferred term	Frequency
very common >10% -100%; com	nmon >1% -10%; uncommon >0.1%-1%	; rare < 0,1%
Infections and infestations	bacterial and viral infection (incl. infection, cellulutis, bronchitis, sinusitis, herpes zoster, herpes simplex)	very common
	upper respiratory tract infection	very common
	urinary tract infection (incl. dysuria, urinary frequency, urinary tract infection, urinary urgency)	very common
	pharyngitis	very common
	pneumonia (incl. interstitial pneumonia)	very common
	rhinitis	common
	folliculitis	common
	sepsis (incl. sepsis, septic shock)	common
Blood and lymphatic system disorders	thrombocytopenia	very common
	anemia	very common
	neutropenia	very common
	leukopenia	very common
	lymphocytopenia	very common
Immune system disorders	allergic/hypersensitivity reactions	common
Metabolism and nutrition disorders	hypokalaemia	very common
	anorexia	very common
	hyperglycemia/diabetes mellitus	very common
	hypercholesterolaemia	very common
	hyperlipaemia	common
	dehydration	common
	hypocalcaemia	common
	hypophosphataemia	common
Psychiatric disorders	insomnia	very common
	anxiety	very common
	depression	common
Nervous system disorders	dysgeusia	very common
	ageusia	common
	dizziness	common
	paraesthesia	common

Eye disorders	conjunctivitis	common
	eye haemorrhage	common
Vascular disorders	thrombosis (incl. deep venous thrombosis, thrombosis)	common
	hypertension	common
Respiratory, thoracic and mediastinal disorders	dyspnea	very common
	epistaxis	very common
	cough	very common
	pneumonitis	common
Gastrointestinal disorders	diarrhea	very common
	nausea	very common
	vomiting	very common
	stomatitis (incl. aphtous stomatitis, mouth ulceration, stomatitis, glossitis, oral pain))	very common
	abdominal pain	very common
	gingivitis	common
	dysphagia	common
	bowel perforation	common
	gastrointestinal haemorrhage (incl. gastrointestinal haemorrhage, rectal haemorrhage)	common
	gingivitis	common
	gastritis	common
Skin and subcutaneous tissue disorders	rash	very common
	pruritus	very common
	nail disorders	very common
	dry skin	very common
	acne	common
	moniliasis	common
	fungal dermatitis	common
	ecchymosis	common
Musculoskeletal and connective tissue disorders	arthralgia	very common
	back pain	very common
	myalgia (incl. muscle cramps, leg cramps, myalgia)	very common
General disorders and administrative site conditions	oedema (incl. oedema, facial oedema, peripheral oedema, scrotal oedema, genital oedema, generalised oedema)	very common
	pain	very common

	asthenia	very common
	pyrexia	very common
	mucositis	very common
	chills	very common
	chest pain	common
Investigations	AST increased	common
	ALT increased	common
	blood creatinine increased	common

Further details of the side effect profile of temsirolimus can be found in the current version of the "Fachinformation". The 'Fachinformation' will be filed in the Investigator Site File and will be the relevant reference document for the side effect profile. In case of updates, no amendment of the study protocol will be written unless changes in therapy or other recommendations result from the new 'Fachinformation'. The updated 'Fachinformation' will be filed in the Investigator Site File.

8.12.2 Standard cytotoxic therapy (cytarabine, daunorubicin and mitoxantrone)

For information of all known adverse drug reactions please refer to the "Fachinformationsverzeichnis Deutschland" in its latest version.

9 STUDY OUTCOME AND STATISTICAL ANALYSIS

9.1 Power and Sample Size Calculation

A single stage design with fixed sample size was chosen. The accrual time will be 24 months with a follow-up time of 12 months (see 7.4).

Let m_0 and m_1 be the median event free survival times for the control and the temsirolimus arm respectively. The Logrank test will be used to test the null hypothesis

 $H_0: m_1/m_0 = 1$

against the two-sided alternative

 H_1 : $m_1/m_0 \neq 1$.

The allocation ratio was determined to be $n_1/n_0 = 1.0$.

A total of 146 evaluable patients are expected to be sufficient to detect a prolongation of the median EFS from 7 to 11.75 months with a power of 80% and a significance level of α =0.05. This change is considered to be clinically relevant. Under the assumption of loss to follow-up, or of alternate post-remission treatment (i.e. bone marrow transplantation), or protocol violation in up to 54 patients, total accrual to the phase II part of this trial is planned for 200 patients (100 per arm).

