4.2 Benefit / risk ratio

Patients eligible for this trial have a risk of treatment failure with standard chemotherapy of 70-80% at two years. Treatment failure is not compatible with long-term survival in these elderly patients. Included in these numbers are disease-related events (refractory disease, relapse) and treatment-related mortality that has to be expected to reach up to 10% in this patient group. The risk of this trial is that addition of temsirolimus to the standard treatment increases treatment-related mortality due to higher toxicity. Therefore the optimal temsirolimus dose level will be tested in the run-in part of this study, which will precede the randomized main part.

The possible benefit of the trial is to decrease the rate of treatment failure in the trial population. For a single patient, this could result in increased life-span, ideally without evidence of leukemia. Given the extensively high rate of treatment failure and the high toxicity of the currently available standard therapy, the medical need for novel, rational therapeutic approaches for this patient population is overwhelming. As pointed out above, the molecular rationale for the therapeutic administration of temsirolimus in AML is well founded. Thus, the Benefit/Risk ratio for a patient to participate in this trial seems very favorable.

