9.2 Statistical Analysis Plan

The statistical analysis will be performed according to the intention to treat principle (ITT analysis). This means that every patient included into the study and randomized to one treatment arm will be evaluated in that arm, even if he does not receive study-medication, or if any other violations of the study protocol occur.

- The primary endpoint (median EFS) will be compared between both treatment arms using two-sided stratified Logrank test. This part of the analysis is considered as confirmatory.
- Analyses of secondary endpoints will include, among others, relapse free survival, early
 response rate, morphologic and molecular CR-rate, overall survival, minimal residual
 disease, evaluation of potential biomarkers indicating the course of disease, including
 genetic, epigenetic, transcriptional and protein markers as well as indicators of autophagy
 in leukemic blasts, bone marrow, peripheral blood cells, serum and plasma
- Patients undergoing allogenic bone marrow transplantation are censored for EFS and OS at the time of bone marrow transplantation.

• In addition to the ITT-analysis a per protocol analysis (PP-analysis) will be performed. This analysis will include only those patients who could be treated with full adherence to the protocol. Besides this, the PP-analysis will parallel the ITT-analysis.

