	day 42 after last chemotherapy • CTCAE Grade 3 non-hematologic temsirolimus-related adverse event (excluding hypertension and nausea / vomiting which is not medically managed) Patients must be evaluable for DLT assessment. Patients with early death during induction due to events unrelated to temsirolimus treatment e.g infection will not be considered as DLT. Patients with neutropenia of thrombocytopenia due to refractory or recurrent AML will not be considered for DLT. If such cases occur additional evaluable patients will be included.		
	If < 2 out of 6 patients experience DLT at dose level 2 during induction chemotherapy, dose level 2 will be chosen for temsirolimus during the main part. If > 2 of 6 patients experience DLT at dose level 2 and < 2 out of 6 patients experience DLT at dose levels 1 will be chosen for temsirolimus during the main part. If 2 out of 6 patients experience DLT at dose level 2 and \leq 2 patients experience DLT at dose level 1, the Data Safety Monitoring Board (DSMB) may opt to include additional 6 patients in dose level 2 of the run-in phase. Depending on the results, the DSMB may consider an additional dose level to		
	be tested in 6 additional patients or terminate the trial. Main part A total of 146 evaluable patients are expected to be sufficient to detect a prolongation of the median EFS from 7 to 11.75 months with a power of 80% and a significance level of α =0.05. Under the assumption of loss to follow-up or of alternate post-remission treatment (i.e. bone marrow transplantation), or protocol violation in up to 54 patients, total accrual to the phase II part of this trial is planned for 200 patients (100 per arm).		
Sample size	Run-in-part: A maximum of evaluable 18 patients will be enrolled Main part: 200 patients will be enrolled (100 in each treatment group)		
Trial duration	- First patient in: - Last patient in: - Last patient in: - Recruitment: - Treatment: - Follow up: - Trial duration: - End of study: January 2nd, 2014 - 2014 - January 2nd, 2014 - January 2nd, 2014 - January 2nd, 2014 - January 2nd, 2016		

Performance Status

ECOG		Karnofsky	
Score	Description	Score	Description
disease performance without	Fully active, able to carry on all predisease performance without restriction.	100	Normal, no complaints, no evidence of disease.
		90	Able to carry on normal activity; minor signs or symptoms of disease.

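### The 80% power in 9.1 assumes constant-hazard EFS with about 9% event-free at two years; 4.2 implies about 20–30%, and if that approximates EFS the power for the stated median target falls well short

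*Protocol*

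**What the plan says.** Protocol 9.1 plans a fixed sample size. It expresses the effect as a ratio of medians and states that "A total of 146 evaluable patients are expected to be sufficient to detect a prolongation of the median EFS from 7 to 11.75 months". The error rates given there are 80% power and a level of 0.05. Allocation is 1:1, and "The accrual time will be 24 months with a follow-up time of 12 months". Up to 54 patients may be lost, transplanted or in violation of the protocol, so 200 are enrolled. Section 9.2 says that EFS "will be compared between both treatment arms using two-sided stratified Logrank test", by intention to treat. The synopsis repeats the target and the power. Neither place names a survival distribution, a hazard ratio or a required number of events.

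Section 4.2 states: "Patients eligible for this trial have a risk of treatment failure with standard chemotherapy of 70-80% at two years". It adds: "Included in these numbers are disease-related events (refractory disease, relapse) and treatment-related mortality". Section 9.5 defines EFS as time to treatment failure, relapse from CR or CRi, or death from any cause. Section 3 says that the control-group EFS of an earlier trial was used for the power calculation, without giving that curve.

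**The concern.** A ratio of medians equals an inverse hazard ratio only when hazards are constant. A constant hazard with a 7-month median makes the two-year EFS a fixed number, which can be compared with the protocol's statement about two-year failure. The two disagree by a factor of two to three.

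If the two-year figure in 4.2 is close to EFS, the control curve must fall early and then flatten. Two things follow: fewer events occur within 12–36 months of observation, and moving the median from 7 to 11.75 months takes a weaker hazard ratio than 0.596. Both lower the power of the confirmatory test. A non-significant result could then be read as evidence against the 11.75-month effect that 9.1 calls clinically relevant, although the trial had a limited chance of detecting it.

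**Working it through.** **Inputs.** Medians 7 and 11.75 months, 80% power, α = 0.05, 1:1 allocation, 24 months' accrual plus 12 months' follow-up (all 9.1); two-sided logrank test (9.1, 9.2); two-year failure risk 70–80% (4.2). Accrual is taken as uniform, so observation is uniform over 12–36 months.

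**Step 1: reproduce 146.**
- HR = 7/11.75 = 0.596; ln HR = −0.518.
- Events (Schoenfeld) = 4(1.960 + 0.842)²/0.518² = 117.0, or 118 when rounded up.
- Mean event probability under constant hazards: 0.884 control, 0.736 temsirolimus, average 0.810.
- N = 118/0.810 = 145.7, so 146.
- Enrolment: 54/200 = 27%, and 146/(1 − 0.27) = 200.

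Other common forms miss 146: Freedman gives 152, Lachin–Foulkes 150, and a fixed 12 months of follow-up for everyone 196. The plan's figure is therefore arithmetically sound, and it is a constant-hazard figure.

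**Step 2: the two-year EFS this implies.** 0.5^(24/7) = 9.3% event-free, or 90.7% failed, against 70–80% failed in 4.2.

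**Step 3: power on a curve through both figures.** The protocol gives only two points, so a shape has to be assumed. Take a Weibull control curve S(t) = exp(−ln2·(t/7)^k) with S(24) = s, so that k = ln(ln(1/s)/ln2)/ln(24/7). Under proportional hazards:
- moving the median to 11.75 months requires HR = (7/11.75)^k;
- keeping HR 0.596 gives a temsirolimus median of 7·(11.75/7)^(1/k).

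Power = Φ(|ln HR|·√events/2 − 1.96).

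Target: median 11.75 months

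| s | k | HR | Events, N = 146 | Power, 146 | Power, 200 fully followed |
|---|---|---|---|---|---|
| 0.20 | 0.684 | 0.702 | 106 | 44% | 57% |
| 0.25 | 0.563 | 0.747 | 100 | 31% | 40% |
| 0.30 | 0.448 | 0.793 | 95 | 20% | 26% |

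Target: HR 0.596

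| s | Implied median (months) | Events, N = 146 | Power, 146 | Power, 200, no loss | Power, 200, 27% loss |
|---|---|---|---|---|---|
| 0.20 | 14.9 | 102 | 74% | 86% | 83% |
| 0.25 | 17.6 | 94 | 71% | 84% | 81% |
| 0.30 | 22.2 | 87 | 68% | 81% | 78% |

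The last column assumes exponential loss reaching 27% by 24 months, which gives about 127 down to 112 events.

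**Step 4: sensitivity, 146 patients.**
- *Curve shape, median target.* A hazard change at month 7 gives 37% (s = 0.20) and 15% (s = 0.30). Simulated cure-type curves give about 39–64% and 22–34%.
- *Two-year level, Weibull.* At s = 0.15, power is 61% for the median target and 77% for HR 0.596. At s = 0.10 it is 78% and 80%.

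**The case against.** The strongest reply is that 4.2 is not a design input. It gives a rounded failure risk within a benefit/risk argument and never calls it EFS. Its listed components include treatment-related mortality only, whereas EFS counts every death, so two-year EFS may lie below 20–30%. Section 3 gives CR in about 50% of patients over 60 and long-term disease-free survival of 10–20%. If the latter refers to patients in remission, 0.5 × 10–20% = 5–10% of all patients, which is compatible with 9.3%. This stands: the protocol does not establish that EFS is 20–30% at two years, and near 10% the stated power is almost recovered. It does not remove the inconsistency, because the components in 4.2 are close to the EFS composite and no sentence explains the gap.

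A second reply is that the intention-to-treat analysis uses 200 patients, not 146. This also stands for HR 0.596, where power is about 78–83% even with the planned loss. It does not rescue the 11.75-month target, which stays at 57% or less on the Weibull curves with no loss at all.

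A reader might infer that the sample size calculation contains an arithmetic error. It does not; 146 and 200 both reproduce. A reader might also infer that the protocol's own figures fix the power at 20–74%. They do not: that range merges two different targets and rests on a curve shape that the protocol does not give.

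**Conclusion.** The point holds as an unreconciled planning assumption. The 80% belongs to a constant-hazard curve with 9.3% event-free at two years. If the 70–80% failure risk in 4.2 approximates EFS, the 80% does not hold for a median of 7 versus 11.75 months: about 44% to 20% with 146 patients and 57% to 26% with 200 fully followed, on an assumed Weibull curve. At HR 0.596 the loss is modest (74% to 68% with 146) and planned enrolment roughly makes it good, but that hazard ratio then means a temsirolimus median of about 15–22 months. The direction is the same for every shape tried, and none at 20–30% event-free reached 80% with 146 patients. The exact values do depend on the shape and on how closely 4.2 matches EFS.

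It is tempting to conclude that analysing at 117 events would cure the problem at the price of a few months. The figures do not support this. On the Weibull curves, 117 events give only about 48% to 24% power for 11.75 months. With 146 evaluable patients at HR 0.596, reaching 117 events would take about 13 (20% event-free) to 63 (30%) months beyond the planned follow-up. Nor does the material support calling for a larger trial, since the two-year EFS is itself unsettled.

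**What to change.** 1. Reconcile 4.2 with 9.1. If the 70–80% is not EFS, correct or relabel it; if it is, say so in 9.1.
2. In 9.1 and the synopsis, state the constant-hazard assumption, the target HR of 0.596 and the roughly 117 EFS events it requires.
3. Restate the power under the two-year EFS finally adopted, separately for HR 0.596 and for a median of 11.75 months, and name the assumed curve shape. The sponsor can take that shape from the control arm already cited as the source of the sizing.

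No increase in enrolment is proposed. The cost is wording, a short recalculation and probably a less favourable stated power for the median target.

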9.2 Statistical Analysis Plan

The statistical analysis will be performed according to the intention to treat principle (ITT analysis). This means that every patient included into the study and randomized to one treatment arm will be evaluated in that arm, even if he does not receive study-medication, or if any other violations of the study protocol occur.

- The primary endpoint (median EFS) will be compared between both treatment arms using two-sided stratified Logrank test. This part of the analysis is considered as confirmatory.
- Analyses of secondary endpoints will include, among others, relapse free survival, early
 response rate, morphologic and molecular CR-rate, overall survival, minimal residual
 disease, evaluation of potential biomarkers indicating the course of disease, including
 genetic, epigenetic, transcriptional and protein markers as well as indicators of autophagy
 in leukemic blasts, bone marrow, peripheral blood cells, serum and plasma
- Patients undergoing allogenic bone marrow transplantation are censored for EFS and OS at the time of bone marrow transplantation.

• In addition to the ITT-analysis a per protocol analysis (PP-analysis) will be performed. This analysis will include only those patients who could be treated with full adherence to the protocol. Besides this, the PP-analysis will parallel the ITT-analysis.

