5.4 Withdrawal of patients

A patient is free to withdraw from the study at any time for any reason without prejudice to his/her future medical care by the physician or at the institution. The Investigator may also withdraw the patient at any time in the interest of the patient's safety. The primary reason for withdrawal must be recorded in the patient's medical record and on the withdrawal form in the Case Report Form (CRF).

Patients eligible for ETAL2 study enrollment may be withdrawn from the TOR-AML trial at any time at the Investigator's discretion. The reason for withdrawal (enrollment into ETAL2 trial) must be recorded on the withdrawal form in the Case Report Form (CRF).

However, these patients should preferably be identified prior to enrollment into the TOR-AML trial and enrolled into ETAL2. Specifically, enrollment into the ETAL2 trial should be considered for patients that fulfill all of the following criteria:

- (1) "fit for allogeneic transplantation", as determined by the investigator
- (2) known high-risk cytogenetics or a probability of CR below 40% (as determined by the AML-score at www.aml-score.org)
- (3) age between 61 and 72 years

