• Death occurring ≥ 7 days following completion of initial chemotherapy (CT); death while cytopenic, with aplastic bone marrow and without evidence of persisting leukemia

Death from indeterminate cause:

Death occurring before completion of therapy, or < 7 days post CT; Patients who die ≥ 7 days post CT with no PB blasts, but bone marrow examination not performed or not evaluable; Patients who do not complete the first course of therapy

Morphologic relapse:

• Reappearance of blasts post CT in PB or \geq 5% blasts in the bone marrow or development

of extramedullary disease

In addition to these response criteria, incomplete CR (CRi) is defined as:

CR with incomplete recovery (CRi) with neutrophils < 1,000/µl and platelets < 100,000/µl

Treatment failure is defined as:

no morphologic leukemia-free state, no partial remission

In addition, early treatment response at day 15 after start of first induction chemotherapy is defined

as:

Good response: < 5% blasts

Poor response: $\geq 5\%$ blasts

9.5 **Definition of Study Endpoints**

Event free survival (EFS):

Time interval from day 1 of study treatment until treatment failure, relapse from CR or CRi,

or death from any cause, whichever occurs first. The time point at which the patient is

resistant to therapy or survives induction without a CR, CRi or morphologic leukemia-free

state will be recorded.

For a patient with none of these events before the end of study follow-up, observation of EFS

will be censored at the date of his or her last follow-up examination.

Relapse free survival (RFS):

Time interval from the day of documentation of CR until relapse or death from any cause.

Overall survival (OS):

Time interval from day 1 of study treatment to the day of death. For a patient who is not

known to have died by the end of follow-up, observation of OS will be censored on the date

the patient was last known to be alive.

Study protocol, TOR-AML, Final Version 3.1, April 13rd, 2012

63

Complete remission rate (CR rate):

The proportion of patients in complete remission (CR, as defined above) after induction chemotherapy.

Early response rate:

The proportion of patients with a morphologic leukemia-free state (as defined above, < 5% blasts) in the first treatment assessment on day 15 after start of first induction chemotherapy.

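### Censoring EFS and OS at allogeneic transplant (9.2) conflicts with the endpoint definitions (9.5) and does not give the ITT comparison that 9.2 announces

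*Protocol*

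**What the plan says.** All references are to the protocol.

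- **9.2, principle.** "The statistical analysis will be performed according to the intention to treat principle (ITT analysis"). It is then spelled out: "every patient included into the study and randomized to one treatment arm will be evaluated in that arm". Missing study drug or violating the protocol does not change this.
- **9.2, primary test.** EFS "will be compared between both treatment arms using two-sided stratified Logrank test", and this is the only part called confirmatory.
- **9.2, censoring.** "Patients undergoing allogenic bone marrow transplantation are censored for EFS and OS at the time of bone marrow transplantation". No analysis without this rule is stated, and the per-protocol analysis is to run in parallel with the ITT analysis.
- **9.5, OS.** "Time interval from day 1 of study treatment to the day of death". Censoring is only for a patient not "known to have died by the end of follow-up, observation of OS will be censored on the date" last known alive.
- **9.5, EFS.** The events are treatment failure, relapse from remission, and death of any cause. Only patients with none of these are censored, at their last follow-up examination. Transplant is not mentioned.
- **9.1 and 9.3.** 9.1 counts transplant, with loss to follow-up and protocol violation, among the reasons for up to 54 extra patients. 9.3 calls the same 54 loss to follow-up in a quarter of patients.
- **5.4.** "Patients eligible for ETAL2 study enrollment may be withdrawn from the TOR-AML trial at any time", at the investigator's discretion. The criteria for that trial are fitness for transplant, high-risk cytogenetics or a low probability of remission, and age 61 to 72.
- **5.3.4.** The treating centre learns the arm after the second consolidation cycle.
- **7.1.6 and 7.4.** Patients with relapse, study exclusion or refused consent are followed to one year from the start of induction.

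**The concern.** Two sections give different outcomes for the same patient, and one of the endpoints affected carries the confirmatory test. An analyst cannot follow both.

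The rule in 9.2 also conditions on something that happens after randomisation. Transplant depends on fitness, risk group and remission, and after consolidation II it may be decided with the arm known. If temsirolimus changes the remission rate, it can change who reaches transplant. The logrank test and the Kaplan-Meier curves assume that censored patients have the same outlook as comparable patients still under observation. Where that fails, the hazard ratio, the median, or both can be distorted, and the direction cannot be known in advance.

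**Working it through.** **1. The two sections side by side**

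| Course of patient | 9.5 | 9.2 |
|---|---|---|
| Remission, transplant, then relapse | EFS event at relapse | EFS censored at transplant |
| Remission, transplant, then death without relapse | EFS and OS event at death | both censored at transplant |
| Relapse, later transplant, then death | EFS event at relapse, OS event at death | EFS event at relapse, OS censored at transplant |

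**2. The plan's sample size**

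Inputs from 9.1: medians 7 and 11.75 months, two-sided alpha 0.05, power 80%, 1:1 allocation, 24 months accrual, 12 months follow-up. Assumption: exponential survival and uniform accrual, so follow-up runs from 12 to 36 months.

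- HR = 7/11.75 = 0.596; ln HR = -0.518.
- Events (Schoenfeld) = 4 × (1.960 + 0.842)² / 0.518² = 117.03, so 118.
- Event probability = 1 - [exp(-12λ) - exp(-36λ)] / (24λ), with λ = ln 2 / median: 0.884 (control) and 0.737 (temsirolimus), mean 0.810.
- N = 118 / 0.810 = 145.7, so 146. The stated figure reproduces, and 146 / (1 - 0.27) = 200.

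**3. Events and power with 200 patients**

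With no early censoring, 100 × (0.884 + 0.737) = 162 events are expected. Now assume that transplant happens at month 5 in patients who are event-free, is unrelated to prognosis, and does not change the hazard.

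- Event-free at month 5: 100 × (0.6095 + 0.7446) = 135.4.
- Events expected after month 5: 100 × [(0.884 - 0.390) + (0.736 - 0.255)] = 97.4.
- Events lost if n are transplanted: (n / 135.4) × 97.4.
- Power = Φ(0.518 × √events / 2 - 1.96).

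| Transplanted | Events lost | Events left | Power |
|---|---|---|---|
| 0 | 0 | 162 | 91% |
| 20 (10%) | 14 | 148 | 88% |
| 40 (20%) | 29 | 133 | 85% |
| 54 (27%) | 39 | 123 | 82% |

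The last row gives the whole allowance of 54 to transplant, although 9.1 shares it with other causes.

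**4. Bias when there is no treatment effect**

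The protocol gives no transplant rate, so these inputs are assumed: 100 patients per arm, 40% high-risk with three times the hazard, transplant at 3 to 6 months, 11 to 15% transplanted overall, 2,000 runs per scenario (Monte Carlo error about 0.5 points). The table takes a post-transplant hazard ratio of 1.0.

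| Who is transplanted | Censored: HR, type I error | Not censored: HR, type I error |
|---|---|---|
| Unrelated to risk, equal by arm | 1.00, 5.0% | 1.00, 4.8% |
| Mainly high-risk, equal by arm | 1.00, 4.9% | 1.00, 5.1% |
| High-risk, more on temsirolimus | 0.93, 6.9% | 1.00, 5.0% |
| High-risk, more on control | 1.06, 6.5% | 1.00, 4.7% |
| Lower-risk, more on temsirolimus | 1.07, 7.0% | 1.00, 4.6% |

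In the second row the estimated median EFS is about 7.4 months with censoring and 6.9 without.

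With a post-transplant hazard ratio of 0.6, the three arm-dependent scenarios give 0.94, 1.07 and 1.07 with censoring (type I error 6.3 to 7.8%). Without censoring they give 0.97, 1.03 and 0.93 (rejection 5.0 to 8.0%), because that analysis then includes the benefit of transplant itself.

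**5. What one year of follow-up recovers**

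In the 27% case, events between months 5 and 12 number (54 / 135.4) × 100 × [(0.6095 - 0.3048) + (0.7446 - 0.4927)] = 22. So 22 of the 39 lost events fall within one year of starting treatment, and 17 fall later.

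**The case against.** **The rule is deliberate.** It is prespecified, and 9.1 provides for transplant in the sample size. It can be read as targeting the effect that would be seen without transplant. That stands as an explanation, but it does not reconcile 9.2 with 9.5, and neither section names such a target.

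**The ITT wording is not broken.** A reader might infer that 9.2 removes transplanted patients from the ITT set. It does not: nobody changes arm and nobody is excluded, so the sentence on assignment is respected. What is lost is the outcome after transplant.

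**Power is safe.** A reader might infer that the lost events leave the trial underpowered. They do not: even the extreme case keeps 123 events, above the 118 that the plan needs.

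**The bias is conditional and modest.** It rests on assumed inputs. Section 3 says transplant is used more often in younger patients, and this trial enrols from age 61. With balanced use the test keeps its level. This stands. The hazard ratio and the level move only if transplant use differs by arm.

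**ETAL2 is a separate route.** 9.2 does not censor at entry into ETAL2, and 5.4 prefers that such patients be identified before enrolment. This also stands. ETAL2 matters here as evidence that transplant candidacy is tied to prognosis, and because follow-up of withdrawn patients is limited.

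**Conclusion.** The point holds as a contradiction between 9.2 and 9.5 that reaches the confirmatory EFS test, and as a rule that discards post-randomisation outcomes under an ITT label. That part needs no simulation.

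The statistical harm is possible bias, not lost power. On the assumed inputs, balanced but risk-selected transplant moves the estimated median EFS by about half a month (6.9 to 7.4), which matters because 9.2 names median EFS as the primary endpoint. Arm-dependent use moves a null hazard ratio to between about 0.93 and 1.07, with type I error of 6 to 8%. The power figures (82 to 91%) assume exponential survival, 12 to 36 months of follow-up, and no effect of transplant on the hazard.

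The documents do not support a claim that the confirmatory result will be biased, or in which direction: they give no transplant rate and no sign that rates will differ by arm. The textual conflict is certain; the size of the bias is not.

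**What to change.** 1. **9.2.** Remove transplant censoring from the primary EFS and OS analyses, so that events count as 9.5 defines them. Keep transplant-censored EFS and OS as named sensitivity analyses.
2. **7.1.6 and 7.4.** State that EFS and survival status of transplanted and withdrawn patients, including those who move to ETAL2, are collected to the common data cut-off. Deleting the sentence in 9.2 is not enough. One year from induction start is all that these sections secure for patients leaving the study, and transplant in remission is not among their listed triggers.
3. **9.1 and 9.3.** Keep N = 200. Reword the allowance of 54 so that it covers loss to follow-up only, since transplanted and protocol-violating patients stay in the ITT set. Correct the share as well: 54/200 is 27%, not a quarter. If 27% were lost at a constant rate unrelated to outcome, about 126 events and 83% power would remain; with no loss, 162 events and 91%.

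The cost is some extra status follow-up beyond year one and no extra patients. The downside is that the primary estimate then includes any effect of transplant; the sensitivity analysis shows the result with follow-up cut at transplant.
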